8.7.2 Method of Detecting AEs and SAEs

Care will be taken not to introduce bias when detecting AEs and/or SAEs. Open-ended and non-leading verbal questioning of the participant is the preferred method to inquire about AE occurrences.

The method of recording, evaluating, and assessing causality of AE and SAE and the procedures for completing and transmitting SAE reports are provided in Appendix 3 (Section 10.3).

8.7.3 Follow-up of AEs and SAEs

After the initial AE/SAE report, the investigator is required to proactively follow each participant at subsequent visits/contacts. All SAEs will be followed until resolution, stabilization, the event is otherwise explained, or the participant is lost to follow-up (as defined in Section 7.3). Further information on follow-up procedures is provided in Appendix 3, (Section 10.3).

8.7.4 Regulatory Reporting Requirements for SAEs

Prompt notification by the investigator to the Sponsor of a SAE is essential so that legal obligations and ethical responsibilities towards the safety of participants and the safety of a study treatment under clinical investigation are met.

The Sponsor has a legal responsibility to notify both the local regulatory authority and other regulatory agencies about the safety of a study treatment under clinical investigation. The Sponsor will comply with country-specific regulatory requirements relating to safety reporting to the regulatory authority, Institutional Review Boards (IRB)/Independent Ethics Committees (IEC), and investigators.

Investigator safety reports must be prepared for suspected unexpected serious adverse reactions (SUSAR) according to local regulatory requirements and Sponsor policy and forwarded to investigators, as necessary.

Page: 55 of 86

An investigator who receives an investigator safety report describing a SAE or other specific safety information (e.g., summary or listing of SAEs) from the Sponsor will review and then file it along with the Investigator's Brochure and will notify the IRB/IEC, if appropriate, according to local requirements.

8.7.5 Disease-Related Events and/or Disease-Related Outcomes Not Oualifying as AEs or SAEs

Not applicable. For details on AEs and SAEs, refer to Section 10.3.

8.7.6 Pregnancy

Sexually active male participants must agree to use condoms as an effective barrier method and refrain from sperm donation, and/or their female partners of reproductive potential to use a method of effective birth control, during the study treatment and for 1 week after the end of the treatment with darolutamide or enzalutamide.

Pregnancies inadvertently fathered by study participants during the study should be reported and followed up by the investigator using the Bayer Pregnancy Monitoring Forms, if permissible by local legislation.

Pregnancies will be collected from the date of IC signature until 30 days after the last dose of darolutamide is administered.

If an adverse outcome of pregnancy is suspected to be related to study treatment exposure, this should be reported regardless of the length of time that has passed since the exposure to the study treatment.

An induced or a spontaneous abortion is considered to be SAE and should be reported in the same timeframe and in the same manner as all other SAEs.

For all reports, the forms provided are to be used. The report should be submitted within the same timelines as an SAE, although a pregnancy per se is not considered an SAE.

The female partner will also be followed to determine the outcome of the pregnancy, delivery, postpartum recovery and the clinical condition of the offspring during the neonatal period. Information on the status of the mother and child will be forwarded to the Sponsor. Generally, the follow-up will be no longer than 6 to 8 weeks following the estimated delivery date. Any termination of the pregnancy will be reported regardless of fetal status (presence or absence of anomalies) or indication for the procedure.

If a pregnancy is reported, the investigator should inform the Sponsor within 24 hours of learning of the pregnancy and should follow the procedures outlined in Appendix 4 (Section 10.4).

Abnormal pregnancy outcomes (e.g., spontaneous abortion, fetal death, stillbirth, congenital anomalies, ectopic pregnancy) are considered SAEs.

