5.1, Incl criteria 10	More stringent condition related to birth control, and "placebo" removed because not applicable. Old text Sexually active male [] and/or their female partners of reproductive potential to use a method of effective birth control, during the treatment with study intervention/placebo and for 1 weeks after treatment with study intervention/placebo. New text Sexually active male [] and/or their female partners of reproductive potential to use a method of effective birth control, during the treatment with study intervention and for 3	Safety lead suggested to modify the language for effective birth control to be consistent with the more stringent language from ARASENS and ARAMIS.

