5.1 Inclusion Criteria

- 1. Male of \geq 18 years of age.
- 2. Patients must have histologically or cytologically confirmed adenocarcinoma of the prostate.
- 3. Prior treatment with primary radical prostatectomy or definitive RT for localized prostate cancer.
- 4. Patients must have PSA ≥0.2 ng/mL after ART or SRT post-RP or after RP in participants who are unfit for ART or SRT, OR PSA ≥2 ng/mL above the nadir after primary RT only. (RP, radical prostatectomy; ART, adjuvant radiotherapy; SRT, salvage radiotherapy; RT primary radiotherapy)
- 5. The presence of < 5 asymptomatic (symptomatic lesions should be excluded) metastatic lesions (except for visceral metastases), and including extra-pelvic lymph nodes, and > 2 cm pelvic lymph nodes, on conventional or PSMA-PET based imaging methods is permitted. Lesions that need treatment with any opioid based analgetic are considered symptomatic.
- 6. PSADT ≤ 20 months calculated per PCWG3 + RECIST 1.1 per Scher et al. (Scher et al. 2016) and MSKCC nomogram.
- 7. ECOG PS of 0 1.
- 8. Serum testosterone >150 ng/dl.
- 9. Patients must have adequate organ function within 4 weeks before the first dose of study intervention and evidenced by:
 - a. Absolute Neutrophil Count $\geq 1500/\text{mm}^3$
 - b. Platelet count > 100,000/mm³
 - c. Total bilirubin < 1.5 x ULN
 - d. ALT and AST $\leq 1.5 \text{ x ULN}$
 - e. Creatinine < 2.0 X ULN
 - f. Creatinine clearance (CrCl) of ≥ 30 mL/min. CrCl should be calculated at screening using the Cockcroft-Gault formula: Creatinine clearance for males (mL/min) = (140 age in years) x (body weight in kg)/[72 x (serum creatinine in mg/dl)].
 - g. PTT, PT, INR \leq 1.5 x ULN (except if on the aprentic anticoagulation in which case the patient can be enrolled if stable and anti-coagulation levels are appropriate for their condition per good clinical practice).

NOTE: All values must be obtained within 4 weeks prior to first dose of darolutamide.

NOTE: Participants must not have received any growth factor within 4 weeks or a blood transfusion within 7 days prior to the hematology laboratory sample obtained at Screening.

- 10. Sexually active male participants must agree to use condoms as an effective barrier method and refrain from sperm donation, and/or their female partners of reproductive potential to use a method of effective birth control, during the treatment with study intervention and for 3 months after treatment with study intervention.

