10.4 Appendix 4: Questionnaires10.4.1 FACT-P (Version 4)

FACT-P (Version 4)

Below is a list of statements that other people with your illness have said are important. Please circle or mark one number per line to indicate your response as it applies to the past 7 days.

	PHYSICAL WELL-BEING		A little bit	Some- what	Quite a bit	Very much
091	I have a lack of energy	0	1	2	3	4
092	I have nausea	0	1	2	3	4
069	Because of my physical condition, I have trouble meeting the needs of my family	0	1	2	3	4
094	I have pain	0	1	2	3	4
099	I am bothered by side effects of treatment	0	1	2	3	4
con	I feel ill	0	1	2	3	4
097	I am forced to spend time in bed	0	1	2	3	4
_	SOCIAL/FAMILY WELL-BEING	Not at all	A little	Some- what	Quite a bit	Very
088	I feel close to my friends		1	2	3	4
692	I get emotional support from my family	0	1	2	3	4
0000	I get support from my friends	0	1	2	3	4
084	My family has accepted my illness	0	1	2	3	4
085	I am satisfied with family communication about my illness	0	1	2	3	4
coss	I feel close to my partner (or the person who is my main support)	0	1	2	3	4
qı	Regardless of your current level of sexual activity, please answer the following question. If you prefer not to answer it, please mark this box and go to the next section.					
687	I am satisfied with my sex life	0	1	2	3	4

Seglish (University Deposits 1997, 1997

Page: 74 of 86

FACT-P (Version 4)

Please circle or mark one number per line to indicate your response as it applies to the past 7 days.

_	EMOTIONAL WELL-BEING	Not at all	A little bit	Some- what	Quite a bit	Very much
080	I feel sad	0	1	2	3	4
080	I am satisfied with how I am coping with my illness		1	2	3	4
060	I am losing hope in the fight against my illness	0	1	2	3	4
084	I feel nervous	0	1	2	3	4
065	I worry about dying	0	1	2	3	4
088	I worry that my condition will get worse	0	1	2	3	4
	FUNCTIONAL WELL-BEING	Not at all	A little bit	Some- what	Quite a bit	Very much
orn.	FUNCTIONAL WELL-BEING I am able to work (include work at home)	at all				
OF2		at all	bit	what	a bit	much
	I am able to work (include work at home)	at all 0	bit 1	what	a bit	much 4
OP2	I am able to work (include work at home)	0 0 0	bit 1 1	what	a bit	much 4 4
OP2	I am able to work (include work at home)	0 0 0 0	l 1 1	what	3 3 3	4 4 4
OPS OPS	I am able to work (include work at home) My work (include work at home) is fulfilling I am able to enjoy life I have accepted my illness	0 0 0 0	1 1 1 1	2 2 2 2	3 3 3 3	4 4 4 4

Registe (Universal)
19 November 2001

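### Protocol 8.7.6 ends contraception 1 week after treatment, while inclusion criterion 10 requires 3 months

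*Protocol*

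**What the plan says.** **Duration.** Protocol 8.7.6 requires contraception "during the study treatment and for 1 week after the end of the treatment with darolutamide or enzalutamide". Criterion 10 in 5.1 requires it "during the treatment with study intervention and for 3 months after treatment with study intervention". Section 10.5.2.1 (Male participants) gives no duration of its own and refers to the time frame in 5.1. The summary of changes records that criterion 10 used to read "during the treatment with study intervention/placebo and for 1 weeks after treatment with study intervention/placebo", and that it was changed on the safety lead's suggestion "to be consistent with the more stringent language from ARASENS and ARAMIS". That log describes superseded text and is cited here only for the origin of the 1-week value.

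**Pregnancy collection.** Section 8.7.6 also states: "Pregnancies will be collected from the date of IC signature until 30 days after the last dose of darolutamide is administered". The same section, without naming a drug, asks for reporting of pregnancies fathered during the study, and for the sponsor to be told of a reported pregnancy within 24 hours of the investigator learning of it. It places no time limit on adverse outcomes suspected to be related to exposure.

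**Method.** Criterion 10 opens "Sexually active male participants must agree to use condoms as an effective barrier method and refrain from sperm donation, and/or their female partners", so a condom and a partner's effective method are joined by and/or; 8.7.6 uses the same construction. For a non-abstinent man whose non-pregnant partner could conceive, 10.5.2.1 asks for both a condom and a partner method failing in less than 1% per year.

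**Pointer.** For pregnancy procedures 8.7.6 sends the investigator to Section 10.4, which is now headed "10.4 Appendix 4: Questionnaires".

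The SAP does not deal with contraception or pregnancy.

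**The concern.** Two live sections give different durations for the same safety obligation. Criterion 10 is what a man agrees to at entry. Section 8.7.6 is where site staff would look when treatment ends or a pregnancy question arises. A site that works from 8.7.6 could tell a participant that contraception may stop after a week, although he agreed to 3 months and the sponsor lengthened the period on safety advice. What is at stake is exposure of a partner or fetus during the remainder of those 3 months.

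The neighbouring sentences in 8.7.6 raise lesser questions: the collection window names one drug of two, the method standard differs from Appendix 5, and the cross-reference leads to the wrong appendix.

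**Working it through.** The plan gives no computed figure to reproduce. The check is a comparison of current texts plus day counts.

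**Step 1: which duration governs.**
- 5.1, criterion 10: 3 months after study intervention.
- 10.5.2.1: the 5.1 time frame, hence 3 months.
- 8.7.6: 1 week after darolutamide or enzalutamide.
- Summary of changes: 1 week was the old value in criterion 10. The log as supplied has no entry for 8.7.6.

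Two of the three current texts agree, and the third matches the value that the amendment removed. The reasonable reading is that 3 months is intended and 8.7.6 was not updated.

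**Step 2: size of the conflict.** Three calendar months run from 89 days (1 February to 1 May in a non-leap year: 28 + 31 + 30) to 92 days (1 July to 1 October: 31 + 31 + 30).
- Shortfall = 3 months − 7 days: 89 − 7 = 82 days; 92 − 7 = 85 days.
- In weeks: 82/7 = 11.7; 85/7 = 12.1. About 12 weeks.

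**Step 3: pregnancy collection.** The stated window ends 30 days after the last darolutamide dose.
- Part of the contraception period beyond it: 89 − 30 = 59 days; 92 − 30 = 62 days.
- This is the most that can lie outside the window for a darolutamide-treated man, not the usual gap. Under 4.1.3 and Section 7, men who stop early are expected to stay in active follow-up to week 52, and pregnancies fathered during the study are reportable. A man who stops more than 3 months before week 52 and stays in follow-up has no gap.
- What remains is a pregnancy after day 30, after study participation has ended, with no suspected related outcome.
- A man whose only drug is enzalutamide has no end point under the 30-day sentence. The planned enzalutamide arm is 20 men (9.2.2), but the randomized phase is conditional on the lead-in result. In the lead-in phase every treated man receives darolutamide, so the wording has no effect there.

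**Step 4: method and pointer.** A couple relying on a condom alone meets criterion 10 but not 10.5.2.1; a couple using a condom and a highly effective partner method meets both. The correct appendix by title is Appendix 5 (10.5), but its text holds only definitions and contraception guidance. Redirecting the pointer there would still supply no reporting procedure.

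**The case against.** **On duration.** A man must agree to 3 months to be eligible, and Sections 5 and 8 rule out waivers. The stale sentence in 8.7.6 does not release him from that agreement. This stands, and it narrows the realistic harm to mistaken advice at the end of treatment. It does not remove the conflict, because the shorter figure sits in the section that sites would consult for this purpose.

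**On collection.** A reader might infer that the 59 to 62 days beyond day 30 are an error in themselves. The documents do not support that. No text requires the collection window to equal the contraception window, and 30 days matches both the post-dose adverse event window in the Schedule of Activities and the timing of the end-of-treatment visit. A reader might also infer that enzalutamide-only men are outside pregnancy reporting altogether. They are not: the provisions on pregnancies fathered during the study, on 24-hour notification, and on suspected related outcomes apply to either drug. Section 8.7.1 also requires notification of related serious events learned of after discharge, and 8.7.6 classes abnormal pregnancy outcomes as serious. What survives is that one sentence names one drug where its neighbour names two.

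**On method.** A reader might infer that the stricter Appendix 5 rule is the binding one and criterion 10 is wrong. The documents do not show which is intended. Criterion 10 was deliberately revised toward two other darolutamide trials, and Appendix 5 carries text that cannot apply to an all-male trial, such as women stopping hormone replacement before enrollment. This is a query to the sponsor, not an established error.

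**Conclusion.** The duration conflict is real and lies in current text: 1 week in 8.7.6 against 3 months in 5.1 and, by reference, 10.5.2.1. The difference is 82 to 85 days, about 12 weeks. That 3 months is the intended value rests on the two agreeing sections and on the recorded history of the 1-week figure; the day counts assume calendar months. The documents do not say how many participants will have a partner who could become pregnant, and the number may be zero. There is no effect on the analysis, power or sample size.

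The single-drug wording of the collection window is a secondary drafting gap that matters only if the randomized phase opens. The length of that window is not shown to be wrong. The method difference and the pointer are points for clarification.

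**What to change.** In Protocol 8.7.6:
- **Main change.** Replace the 1-week period with 3 months after the last dose of either drug, by cross-reference to 5.1 so that the figure stands in one place.
- **Secondary.** In the collection sentence, change darolutamide to study intervention. The sponsor may decide whether to extend 30 days to 3 months; the present provisions do not make this necessary.

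Queries for the sponsor:
- Choose one contraceptive method standard and use it in 5.1, 8.7.6 and 10.5.2.1. The Appendix 5 rule is the more cautious choice, but aligning Appendix 5 to criterion 10 would also remove the difference.
- Correct the pointer to Section 10.4, and make sure that wherever it leads contains a pregnancy-reporting procedure, since Appendix 5 as written has none.

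The cost is wording in the next amendment: one sentence for the main change and a term for the secondary one, with short edits if the queries are taken up. No visit, sample size or analysis changes. The consent form was not available, so its stated duration should be checked against 5.1 at the same time.

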8.7.7 Adverse Events of Special Interest

There are no adverse events of special interest in this study.

Page: 56 of 86

8.7.8 Management of Overdose

8.7.8.1 Darolutamide

For this study, any dose of darolutamide greater than 600 mg twice daily within a 24-hour time period will be considered an overdose.

The highest dose of darolutamide studied clinically was 900 mg twice daily, equal to a total daily dose of 1800 mg. No dose limiting toxicities were observed with this dose.

Considering the saturable absorption and the absence of evidence for acute toxicity, an intake of a higher than recommended dose of darolutamide is not expected to lead to toxicity.

Therefore, in the event of intake of a higher than recommended dose, it is suggested that darolutamide treatment be continued with the next dose as scheduled.

There is no specific antidote for darolutamide, and symptoms of overdose are not established. No specific information is available on the treatment of overdose of darolutamide. In the event of overdose, the participant should be observed closely for signs of toxicity. Appropriate supportive treatment should be provided if clinically indicated.

Clarification as to intentional or accidental overdose should be reported.

For detailed guidance on overdosing, please refer to the most current version of the IB for darolutamide.

8.7.8.2 Enzalutamide

For detailed guidance on overdosing please refer to the prescribing information for enzalutamide (enzalutamide prescribing information).

8.7.9 In the event of an overdose of study intervention

In the event of an overdose, the investigator should:

- Contact the Medical Monitor immediately.
- Closely monitor the participant for any AE/SAE and laboratory abnormalities for at least 3 days.
- Obtain a plasma sample for PK analysis within 3 days from the date of the last dose of study intervention if requested by the Medical Monitor (determined on a case-by-case basis).
- Document the quantity of the excess dose and duration of the overdose as well as the circumstances (e.g., intentional, accidental/administration error) in the CRF.
- Any overdose or incorrect administration of study intervention should be noted on the Study intervention Administration Electronic Case Report Form (eCRF).
- Adverse events associated with an overdose or incorrect administration of study intervention should be recorded on the Adverse Event eCRF.

Decisions regarding dose interruptions or modifications will be made by the investigator in consultation with the Medical Monitor based on the clinical evaluation of the participant.

8.8 Physical Examinations

A complete routine physical examination will be conducted at baseline and at EOT visit. Weight will also be measured and recorded.

Investigators should pay special attention to clinical signs related to previous serious illnesses.

8.8.1 Vital Signs

Page: 57 of 86

Vital signs will be measured and will include temperature, systolic and diastolic blood pressure, and pulse. Please refer to Section 1.5 Schedule of Activities (SoA), Sampling and Assessments.

8.8.2 Electrocardiograms

Triplicate 12-lead ECG will be obtained as outlined in the SoA (see Section 1.5) using an ECG machine that automatically calculates the heart rate and measures PR, QRS, QT, and QTc intervals. Refer to Section 7 for QTc withdrawal criteria and any additional QTc readings that may be necessary.

At each time point at which triplicate ECG are required, 3 individual ECG tracings should be obtained as closely as possible in succession, but no more than 2 minutes apart. The full set of triplicates should be completed in less than 4 minutes.

8.8.3 Clinical Safety Laboratory Assessments

See Appendix 2 (Section 10.2) for the list of clinical laboratory tests to be performed and refer to the SoA (Section 1.5) for the timing and frequency.

The investigator must review the laboratory report, document this review, and record any clinically relevant changes occurring during the study in the AE section of the CRF. The laboratory reports must be filed with the source documents. Clinically relevant abnormal laboratory values or test results must be identified through a review of values outside of normal ranges/clinical notable ranges, significant changes from baseline or the previous visit, or values which are considered to be non-typical in patient with underlying disease.

All laboratory tests with values considered clinically relevant abnormal during participation in the study or within 30 days after the last dose of study intervention should be repeated until the values return to normal or baseline or are no longer considered clinically significant by the investigator or medical monitor. All protocol-required laboratory assessments, as defined in Appendix 2, Section 10.2, must be conducted in accordance with the SoA (Section 1.5).

If laboratory values from non-protocol specified laboratory assessments performed at the institution's local laboratory require a change in participant management or are considered clinically relevant by the investigator (e.g., SAE or AE or dose modification), then the results must be recorded in the CRF.

8.9 Pharmacokinetics

PK parameters are not evaluated in this study.

8.10 Pharmacodynamics

Pharmacodynamic parameters are not evaluated in this study.

8.11 Genetics

Genetics are not evaluated in this study.

